#### **Brief Interventions for Pittsburgh Site**

Research counselors at the Crescenz VAMC in Philadelphia will perform all BI's for Veterans recruited from the Pittsburgh site. These BI's will follow the same structure as BI's that occur at the Crescenz VA, they will be over the phone and take about 20 minutes to complete.

#### **Brief Intervention Only Group (BIO)**

This group only receives a Brief Intervention (BI) that is recommended in response to risky alcohol use. Participants in this group will have 6 study visits as described below.

#### **Prevention Intervention Group**

Participants in this group also will get a Brief Intervention. In addition, they will get text messages as described in the next section.

**PI Overview.** We have designed an adaptive monitoring intervention, delivered primarily through text messages and brief telephone calls that can provide extended prevention services for Veterans engaging in risky/hazardous alcohol use. These services address motivational issues and identify more effective ways to cope with stress and other factors that trigger unsafe alcohol use. The intervention is adaptive in two ways. Veterans who reduce alcohol use to safe levels will be placed in a monitoring track, which consists of tailored text messages (see appendix which contains examples of text messages to be used) and brief monthly telephone contacts. Conversely, Veterans who continue to use alcohol at hazardous levels will instead be placed in a track that provides tailored text messages and more frequent telephone calls. In addition to monitoring, these calls provide further prevention/brief intervention services to help the Veteran reduce alcohol use to non-hazardous levels and reduce the use of benzodiazepines and other potentially hazardous drugs. Phone calls will be audio recorded to ensure adherence of the Research prevention counselors to the manuals. We will remind subjects that calls are being recorded and they can refuse the recording, but still participate in the research call.

The Wellpass system will automatically send text messages to Veterans either within messaging windows or at specific days and/or times depending on the goal of the message (e.g. appointment reminder vs. motivational message vs. just-in-time support for at-risk Veterans). On average, Veterans will receive between 1-14 tailored text messages per week, depending on whether they are reducing

drinking to below risky levels. In addition to sending tailored messages as described above, the SMS system will conduct on average weekly ecological assessments. (Ecological assessments are research questionnaires that happen in the “real world.” Ours will entail text messages such as: “Have you met the goal you set for yourself over the past week? Please respond 1 (not at all), 2 (somewhat) or 3 (mostly).” These are different from the motivational messages and are used to track progress and inform phone counseling sessions.) Veterans who are having trouble meeting their goals will receive more assessment messages. Veterans who initially reduce alcohol use to safe levels and are therefore placed in the monitoring track will transfer over to the more intensive prevention track if their alcohol use increases to risky levels at some point in the 12-month intervention. Veterans whose alcohol or drug use escalates to DSM-V moderate to severe substance use disorder levels will be given a referral to specialty care and their progress will be evaluated at regular follow-up visits.

Although the research counselors will be able to alter the messaging frequency and scripts based on the progress of the Veteran, decision support rules based on change will help guide messaging content and frequency to reduce research counselor burden. The system will alert research counselors to reductions in motivation or other red flags that may indicate the Veteran needs more support and will include proactive “help messages” for Veterans in the moment, which will trigger just-in-time messages and system alerts. In addition, Veterans can decide on the minimum and maximum number of messages they wish to receive per week. The text message conversations between our research counselors and the study participant will also be recorded and kept in an encrypted database.

All participants will be using their own cell phones during their participation in the study. We will instruct participants to inform us if they lose/damage their phone. However, we will not replace Veterans’ personal cell phones. If data security is breached, we will follow VA and HIPAA mandatory disclosure procedures. If data is lost but not breached (e.g. to server malfunction), we will assess the situation and alert the study sponsor.

#### **Study visits:**

In addition to the intervention, all participants will be seen at 3, 6, 9, 12, and 18 months post baseline for research follow ups. Participants enrolled after 4/1/2019 will only be seen at 3, 6, 9, and 12 months post baseline for research follow ups. These will be done at the CMCVAMC and will take approximately 1.5 hours. The schedule of assessments (all of which are for research purposes only and not part of standard care) is as follows: SCID and MINI (B); Blood samples (%dCDT and GGT) (B and 18m); Time Line Follow-Back, SIP (B, 3, 6, 9, 12, 18); Drug urine toxicology tests (B, 3, 6, 9, 12, 18); Self-efficacy, Coping, Social Support, Readiness to Change, pain, depression, quality of life (B, 3, 6, 9, 12, 18).

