- 2.2. Describe how randomization or other treatment assignment will be made. **Veterans who meet criteria for participation will be randomly assigned to one of the two treatment conditions. Urn randomization will be used to balance the groups on three factors: gender, benzodiazepine or other drug use, and age. We will also be blocking on whether the person admits use or not when we do the randomization, so we get equal numbers of non-users in each condition. Urn randomization is a kind of biased-coin randomization where probability of being assigned to a group decreases if the group is overrepresented and increases if the group is underrepresented. As the sample size increases, the randomization shifts from perfect balance to complete randomization.**
- 2.3. For retrospective research studies, provide the "look-back" period. (e.g., December 1, 1999 through December 31, 2008.) **n/a**

3. **Study Duration**

- 3.1. Provide the estimated length of time to enroll all subjects and complete the study. **2.5 years of enrollment, but 5 years total for study start up, enrollment, completion, and analyses.**
- 3.2. Explain the expected duration of subject participation including any follow-up. **18 months for patients enrolled prior to 4/1/2019; 12 months for patients enrolled after 4/1/2019**
- 3.3. Specify the projected date of completion of the proposed study. **5 years from date of funding.**

4. **Drug Information** (If not applicable state, "Not Applicable.") **Not Applicable**

- 4.1. Specify if the drug or biological agent is:
  - 4.1.1. FDA approved
  - 4.1.2. Used for off-label purposes
  - 4.1.3. Not yet FDA approved.
- 4.2. Include the FDA Investigational New Drug (IND) number for all non-FDA approved and off-label drugs, biological agents or nutritional supplements. If not applicable state, "Not Applicable."
- 4.3. Provide all relevant information about the drug
- 4.4. Explain any wash-out periods, rescue medications permitted and any type of medications not permitted while enrolled in the study.
- 4.5. Describe blinding and un-blinding procedures.

- 4.6. Include the dosage, route of administration, previous use, and the safety and efficacy information on any drug used for research purposes.
- 4.7. Describe rationale for the dosage in this study.
- 4.8. Justify why the risks are reasonable in relation to anticipated benefits and/or knowledge.
- 4.9. Describe where drug preparation will be done.

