The primary outcome measure will be rates of risky drinking (i.e., more than 4 drinks at any one sitting or more than 14 drinks/week for men; more than 2 drinks at any one sitting or more than 7 drinks/week for women) within each follow-up period (e.g., months 1-3, 4-6, 7-9, 10-12, 13-18), as determine by the TLFB. Secondary outcomes in the study will be self-reported frequency of heavy drinking days (TLFB), biological measures of alcohol use (%dCDT and GGT), urine toxicology tests to assess other drug use, VA medical records of opioid overdoses, depression, and pain. Outcome data will be analyzed using mixed effect regressions for continuous and categorical data (i.e., SAS) and various packages to examine mediation effects (i.e., MPlus). The alpha level for the primary outcome will be set at 5%.

Data quality will be monitored by random inspection of the completed forms by the research coordinator and any problems detected will be discussed with the PI. The Research prevention counselors will receive standardized training on the interventions, which are all manualized. Adherence to the manuals will be monitored using audiotapes and individual supervision provided by the clinical coordinator. If drift is observed the counselors will be re-trained.

Blind interim analyses of the data will be conducted at two points when 50 and 75% of the sample has been accrued. If the results show statistically overwhelming significant differences between groups, the study will be stopped (or one of the conditions stopped).

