3. If applicable, define the plan for subjects if research shows results such as:

- 3.1. Depression If depression appears to be an issue for a participant, and they are not already receiving treatment, the research staff will consult with [name] for a consult with the participant and a possible referral.
- 3.2. Suicide Participants who indicate any suicidal ideation will be evaluated by [name], [name], or [name] at the CMCVAMC.
- 3.3. Abuse It is anticipated that the Veterans in our study will be engaging in alcohol or drug abuse. [name] will be consulted in the event there is significant change to the Veterans' use status. If the Veteran is in danger in terms of physical abuse or someone else is in danger due to the Veteran abusing them, [name] will be consulted and the appropriate actions will be taken.

4. Statistical Analysis

- 4.1. Include statistical power calculations and the assumptions made in making these calculations. **We consider the primary hypothesis of risky alcohol use, which compares PI and BIO groups on five repeated binary outcomes. We use the sample size formulae of Diggle et al. We expect to have a 20% dropout rate by month 18, and to see a risky drinking rate of 30%. On the assumption of a within subject correlation of 0.3 (resp. 0.4, 0.5), our sample size of 150 per group provides 80% power for a main effect difference of 30% versus 20% (resp. 30% versus 19%, 30% versus 18%) for the BIO versus PI groups.**

**March 2018 Amendment:** Our original power analysis in the grant was very conservative, as it took into account multiple outcome measures and moderation and mediation analyses. We had our statistician re-run the analyses, focusing on the main effect treatment group comparison with the primary outcome measure. If we calculate sample size needed to have 80% power to find a 15- percentage point difference in rates of risky drinking between the two conditions (e.g., 35% control condition vs. 20% experimental condition on risky drinking rate), we need a total of 136 to 162 veterans (depending on different estimates of the correlation between the outcome measure at different follow-up points). If the effect is slightly larger (e.g., 20 percentage point difference), we only need 72 to 84 veterans in total. Therefore, with a combination of the new design we are confident that we will reach a sample size that will be sufficient to at least examine our primary outcome measure.

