- 4.2. Define plans for data and statistical analysis, including key elements of the statistical plan, stopping rules and endpoints.
  - a. Primary objective: The responses for the primary hypothesis comprise five repeated binary measurements per participant indicating risky alcohol use over the follow-up points. Our main analyses will use mixed effects logistic regression models to compare the two groups on the rates of risky alcohol use. We expect that linear and quadratic trends will account for the patterns of use across time. If residual analyses suggest significant lack of fit, we will examine more general time trends using spline specifications. The main explanatory variable will be a binary factor indicating intervention group, together with terms for time trends, and for group by time interactions, if appropriate. Based on analyses of similar data, we expect that a random intercept model, possibly with an autoregressive repeated measures structure, should provide a good fit to the covariance structure of the repeated measures, although we will examine more general specifications, if necessary. The estimated regression coefficients for the group variable, and possibly for group by time interactions, will address our primary hypothesis. We will test whether estimated coefficients are different from zero, and will report estimates and approximate 95% confidence intervals.

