e. Missing values. The mixed effects models will provide valid estimates of treatment efficacy if the missing data meet the ignorable missingness assumption. We will conduct further analyses to assess the sensitivity of our inferences to possible violations of this assumption. First, we will use pattern mixture models (104), defining a categorical variable describing the main patterns of missing data, and including it as a main effect and interaction effect with intervention group in the modes for primary outcomes. Significant differences in the estimated intervention effects across levels of the pattern variable suggest one type of non-ignorable missingness. Second, shared parameter models (104) assume that the repeated responses and repeated binary indicators of missingness have possibly correlated random effects, and significant correlation indicates possible non-ignorability. Finally, semiparametric regression models (106) use inverse probability weighting to extend the validity of GEE models, and provide a different type of sensitivity analysis for the mixed effects models. All three approaches require certain model assumptions, so we will compare the results of the analyses over a range of such assumptions.

X. **Privacy and Confidentiality** (*Privacy refers to persons and to their interest in controlling the access of others to themselves.) (Confidentiality refers to protecting information from unauthorized disclosure or intelligible interception.) (Investigator should contact the Privacy Officer for additional details.)*

1. **Indicate the type of data that will be received by the Principal Investigator. Check all that apply.**

- 1.1.  De-identified – Without any identifiers that could link the data to a specific participant. (Contact Privacy Officer for assistance. If data is coded, it is not considered de-identified.)
- 1.2.  Identified – Linked to a specific participant by identifiers sufficient to identify participants. (See [HIPAA](#) and [Common Rule](#) Criteria for list of identifiers.)
- 1.3.  Coded – Linked to a specific subject by a code rather than a direct identifier. If coded is checked, specify:

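### Missing-data checks in W.4.2.e do not separate the planned absence of month 18 after 4/1/2019 from dropout, and W.4.2.a still counts five measurements for everyone

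*Combined protocol and SAP*

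**What the plan says.** Conduct was changed. M.3.2 gives the duration of participation as "18 months for patients enrolled prior to 4/1/2019; 12 months for patients enrolled after 4/1/2019". O.1 (Study visits) drops the month-18 visit for the later group: "Participants enrolled after 4/1/2019 will only be seen at 3, 6, 9, and 12 months post baseline for research follow ups". O.1.1 repeats this, and the payment schedule in section S agrees.

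The analysis text was not changed to match:

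- W.1 defines the primary outcome "within each follow-up period (e.g., months 1-3, 4-6, 7-9, 10-12, 13-18" months, with no exception.
- W.4.1 assumes: "We expect to have a 20% dropout rate by month 18".
- W.4.2.a says that the responses "comprise five repeated binary measurements per participant indicating risky alcohol use over the follow-up points".
- W.4.2.e plans three sensitivity analyses. The pattern-mixture model works by "defining a categorical variable describing the main patterns of missing data, and including it as a main effect and interaction effect with intervention group". The shared-parameter model assumes that responses and "repeated binary indicators of missingness have possibly correlated random effects". The third is a GEE with inverse-probability weights. The section does not define the patterns, the set of indicators or the weight model, and it does not mention planned absence.

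**The concern.** W.4.2.e reads a difference in intervention effect across missingness patterns, or a correlation between drinking and missingness, as a sign that missingness may not be ignorable. That reading needs the missingness variable to reflect Veterans who were lost. A Veteran with no month-18 visit by design has not been lost. Such a Veteran nevertheless has an empty fifth cell if the checks use the five-window layout of W.4.2.a.

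Two errors can follow. Real dropouts are pooled with Veterans who missed nothing, so informative dropout is harder to see. And enrolment period enters the check disguised as missingness, so a difference between periods can look like informative dropout.

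Such a difference is plausible. All late entrants came in after March 2018, under the criteria in R.2.1.1, which do not require any drinking. At least some of the first 51 Veterans entered under AUDIT-C thresholds. Under O.1, a Veteran not drinking at entry receives neither intervention unless drinking is reported later. Both the rate of risky drinking and the achievable effect could therefore vary with enrolment period. At stake is the robustness statement that accompanies the primary result.

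**Working it through.** **1. Are five windows the plan's working structure?** The repeated-binary formula is n per arm = n(two proportions) × [1 + (m − 1)ρ]/m, with two-sided alpha 0.05 (sidedness is my assumption) and 80% power.

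- Original calculation in W.4.1: 150 × 0.8 = 120 per arm and m = 5 give detectable rates against 30% of 19.7%, 18.8% and 18.1% for ρ = 0.3, 0.4 and 0.5. These round to the stated 20%, 19% and 18%.
- March 2018 calculation, 35% versus 20%: n(two proportions) = 137.9 per arm. I assume an average loss of 10% over follow-up, so the result is divided by 0.9.
  - m = 5, ρ = 0.3: 137.9 × 0.44 / 0.9 = 67.4, so 68 per arm and 136 in total (stated 136).
  - m = 5, ρ = 0.4: 137.9 × 0.52 / 0.9 = 79.7, so 80 per arm and 160 in total (stated 162).
  - m = 4 gives 146 and 170, which do not match.

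The plan's own sizes therefore fit five windows.

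**2. How much of month 18 would be empty by design?** Let f be the share enrolled after 4/1/2019. The documents do not give it. By the March 2018 amendment 42 + 3 + 6 = 51 were randomised, against a target of 200, so f is at most 149/200 = 74.5%. (The R.1 targets sum to 115 + 60 = 175, which gives at most 124/175 = 70.9%.) With 20% dropout among those due at month 18:

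- empty share = f + 0.2(1 − f)
- planned part of the empty cells = f / [f + 0.2(1 − f)]
- month-18 weight if enrolment date is left out of the weight model = 1 / [0.8(1 − f)]

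| f | Empty at month 18 | Planned part | Weight |
|---|---|---|---|
| 0 | 20% | 0% | 1.25 |
| 10% | 28% | 36% | 1.39 |
| 25% | 40% | 62% | 1.67 |
| 50% | 60% | 83% | 2.50 |
| 74.5% | 80% | 94% | 4.90 |

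The two weighting problems are alternatives. With enrolment date in the weight model, late entrants have zero probability of being seen at month 18. Early entrants keep 1.25, but the month-18 data then speak only for them. With the date left out, the weights rise as in the table.

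**3. Effect on the pattern-mixture check.** Illustrative simulation: 20% dropout, N = 150 or 200, f = 25% or 50%, 800 runs per case, Monte Carlo error up to about 2 points. Effect sizes, the difference between periods and the strength of informative dropout were assumed. Entries are the share of trials in which the check was significant.

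| Scenario | Planned absence coded as missing | Scheduled windows only |
|---|---|---|
| Same effect in both periods, ignorable dropout | 4-7% | 7-8% |
| Effect differs by period, ignorable dropout | 50-76% | 5-9% |
| Truly informative dropout | 14-25% | 40-57% |

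The shared-parameter and weighted analyses were not simulated.

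**4. Primary power.** Give each Veteran information m / [1 + (m − 1)ρ], with dropout rising evenly to 20% at month 18. For N = 150 and 35% versus 20%, power at ρ = 0.3, 0.4 and 0.5 is 85%, 79% and 73% if all have five windows, and 84%, 78% and 73% if half have four.

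**The case against.** The strongest reply is that W.4.2.e is silent. It gives no window count and nowhere says that planned absence is dropout. An analyst who follows M.3.2 and O.1 could treat only scheduled visits as capable of being missing. That is true, and a reader should not infer that the plan prescribes the wrong coding. But the only layout the analysis section states is five measurements each, so following it produces the problem. Leaving it open means the coding is chosen after the data are in.

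A reader might also infer that the checks would test enrolment date instead of dropout. The documents do not support that. Missed visits at months 3 to 12 feed every check, and early entrants can still be lost by month 18. Where the effect was the same in both periods, the simulated check gave no false alarm (4-7%). False signals need a difference between periods. That difference is assumed, and it is softened because Veterans enrolled between March 2018 and 4/1/2019 are early entrants under the same broad criteria.

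The dilution also depends on how patterns are cut. If they follow the last visit attended, late completers are mixed only with early entrants lost after month 12. That narrows the problem without removing it.

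Finally, these are sensitivity analyses, and W.4.2.e words their interpretation cautiously. This stands, and it limits the consequence.

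**Conclusion.** The point holds as a conflict between the follow-up schedule and the analysis text that should be corrected. Applied to five windows, the checks mix planned absence with dropout. In the simulated pattern-mixture check this cut power against informative dropout from 40-57% to 14-25%. It raised false signals from 5-9% to 50-76% when the effect differed by period. These figures illustrate direction and rough size. They rest on assumed effects, 20% dropout and a late share of 25% or 50%, and the true share is not stated.

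A reader might go further and conclude that the primary result is biased or underpowered. Nothing here shows that: absence fixed by enrolment date is not informative dropout, and primary power moves by about one percentage point. The damage is confined to the robustness assessment.

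**What to change.** - **W.4.2.a:** state five windows for Veterans enrolled before 4/1/2019 and four for those enrolled after.
- **W.4.2.e:** define missingness, dropout patterns, missingness indicators and weights only over the visits scheduled for that Veteran. Leave month 18 of late entrants out of all of them.
- **W.4.2.e:** include enrolment period as a covariate in the three checks.
- **Reporting:** give month-18 retention with only those scheduled for that visit in the denominator, and report the number enrolled after 4/1/2019.

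The cost is SAP wording and a few lines of code. No new data are needed and conduct does not change.
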